1.5 The immune response to FVIII

1.5.1 The humoral immune response to FVIII

The development of neutralizing antibodies against FVIII (inhibitor formation) is the most severe complication of treatment for haemophilia A patients. Antibodies against functional sites on the FVIII molecule (neutralizing antibodies) can be detected with the Bethesda assay. However, the Bethesda assay cannot detect antibodies against non-functional sites on the FVIII molecule (non-neutralizing antibodies). Alternative techniques such as ELISA [70] can detect a broader range of FVIII-specific antibodies. However, until recently these assays were not able to discriminate between neutralizing and non-neutralizing antibodies, this limited their usefulness in research and clinical practice.

Recently, several studies have shown that antibodies of the IgG4 subclass are more prevalent among patients with neutralizing antibodies, compared to patients with non-neutralizing antibodies. [70] In addition, by using a novel ELISA platform, Hofbauer et al found that they were able to discriminate between neutralizing and non-neutralizing antibodies based on the presence of high-affinity FVIII-specific antibodies. [71]

It is as of yet unclear how FVIII-specific non-neutralizing antibodies could influence the clinical course of disease. One longitudinal study in previously untreated patients (PUPs) by Cannavò et al

found that the presence of non-neutralizing antibodies before the first administration of FVIII was a risk factor for inhibitor formation. [72] There might also be a relationship between the presence of non-neutralizing antibodies and FVIII clearance. Recently, Hofbauer et al [73] conducted a study in which a significant association was found between the presence of FVIII-specific IgG non-neutralizing antibodies and a shorter FVIII half-life.

As of yet, most studies on this subject are small and/or cross-sectional in nature, therefore, the HiN-6 study will assess the prevalence and characteristics of FVIII-specific non-neutralizing antibodies. In addition, The HiN-6 study will also assess the impact of non-neutralizing antibodies on inhibitor development, FVIII activity/antigen levels, joint bleeds and increased FVIII clearance. The HiN-6 will also assess possible misclassification of low-titre inhibitors as non-neutralizing antibodies using a low-titre inhibitor assay (([name], personal communication).

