- Bethesda assay: We will measure the presence of inhibitors using the Bethesda assay with Nijmegen modification. A titre of at least 0.6 Bethesda Units is required to be positive for this assay. The cut-off point for low-titre vs high-titre inhibitors is 5.0 Bethesda Units. [92]
- Low-titre inhibitor assay: To assess the presence of low-titre inhibitors, we will use a lowtitre inhibitor assay. ([name], personal communication)
- ELISA: We will assess the presence and characteristics of FVIII-specific antibodies in our full cohort using a highly sensitive and fully validated ELISA platform developed by Whelan et al.
 [70] In patients who are positive for antibodies using this assay we will characterize the isotype (IgA, IgM and IgG) and for the IgG isotype also the subclass (IgG1 to 4). Samples with confirmed specificity for FVIII will also be assessed for apparent affinity.

The apparent affinities of FVIII-specific antibodies for all immunoglobulin isotypes and IgG subclasses will be assessed using a competition-based ELISA approach by Hofbauer et al. The affinity assessment is based on the availability of antibody for binding to FVIII-coated ELISA plates after competition with FVIII in solution. [71]

• Other laboratory tests such as:

- FVIII and FIX activity using one-stage assay
- FVIII and FIX activity using chromogenic assay
- FVIII and FIX antigen level
- FVIII genotype (if unknown)
- FVIII haplotype
- HLA/IL-10/TNFα/CTLA4/HO-1/FcgR gene variants

Second visit (50 adult participants):

Based on the results of the first analyses, we will draw an additional 50 mL of blood in 50 selected participants during a second visit to the haemophilia treatment centre. This second sample will be only be used for this substudy and will not be stored in the biobank. Blood samples will be used for the following experiments: • **Regulatory T cell count:** Regulatory T cell count will be assessed using both flow cytometry and a quantitative real-time PCR assay developed by Epiontis (Epiontis Treg assay).

Flow cytometry

After stimulation of PBMCs with FVIII, we will quantify all T-cell subsets using flow cytometry. PBMCs will be stained with monoclonal antibodies against cell receptors specific for a certain T-cell subset (e.g. CD4+, CD25high, CD127low, FOXP3+ for T-regulatory cells) [93] and markers of T-cell activation (e.g. CD154) [94].

Epiontis Treg assay

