6.4.4 Validating the iCHEC paediatric bleeding assessment tool in children with haemophilia

Primary objective: to describe the bleeding scores as assessed by a newly developed Paediatric
Bleeding Assessment Tool (iCHEC), in all paediatric patients with haemophilia, and in subgroups
according to haemophilia severity, age and treatment regimen (prophylaxis/on demand).
Determinants: Haemophilia severity, age, treatment regimen.
Population: All paediatric patients with haemophilia.

Endpoint: bleeding scores as assessed by a newly developed Paediatric Bleeding Assessment Tool. **Statistical analysis:** We will use descriptive statistics where appropriate.

6.5 Studies assessing immunological mechanisms that may lead to inhibitor formation in patients with haemophilia A

6.5.1 Assessing the relationship between FVIII-specific non-neutralizing antibodies and inhibitor formation:

Primary objective 1: To assess the prevalence of FVIII-specific non-neutralizing antibodies (NNAs) among non-inhibitor patients with severe, moderate and mild haemophilia A in the Netherlands.
Study design and population: A cross-sectional study design will be used. The population will consist of all haemophilia A patients without current inhibitors in the Netherlands.

Determinant: Disease severity (mild, moderate and severe) will be used as the determinant. **Endpoint:** The prevalence of non-neutralizing antibodies among non-inhibitor patients with haemophilia A in the Netherlands will be used as the endpoint. The Bethesda assay will be used to assess inhibitor presence. If negative, the presence and characteristics of NNAs will be assessed using an ELISA platform developed by Whelan et al. [70]

Statistical analysis: 95% confidence intervals for the prevalence (which is a binomial proportion) will be calculated by using the exact Clopper-Pearson method.

Primary objective 2: To characterize all FVIII-specific antibodies with respect to Ig class, IgG subclass and affinity, and to evaluate whether some of these characteristics are more associated with having neutralizing antibodies (inhibitors) rather than non-neutralizing antibodies (NNAs).

Study design and population: A cross-sectional study design will be used. The population will consist of all haemophilia A patients with neutralizing FVIII-specific antibodies(inhibitors) or non-neutralizing FVIII-specific antibodies (NNAs). Patients without any FVIII-specific antibodies will be excluded from

HiN-6 study

this analysis.

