Determinants: FVIII genotype and family history of haemophilia/inhibitors as well as other potential genetic determinants such as HLA, IL-10, TNF α , CTLA4, HO-1 and FcgR gene polymorphisms. **Potential confounders:** See determinants

Endpoint: The presence of neutralizing FVIII-specific antibodies (inhibitors) or non-neutralizing FVIII-specific antibodies (NNAs) will be used as the endpoint.

Statistical analysis: The relationship between the determinants and the presence of neutralizing FVIII-specific antibodies (inhibitors) or non-neutralizing FVIII-specific antibodies (NNAs) will be explored using logistic regression.

Secondary objective 3: To evaluate the association between non-neutralizing antibodies (NNAs) and bleeding frequency in patients with severe haemophilia A.

Study design and population: A cross-sectional study design will be used. The population will consist of all haemophilia A patients with non-neutralizing FVIII-specific antibodies (NNAs) and all haemophilia A patients without any antibodies. Haemophilia A patients with neutralizing antibodies (inhibitors) are excluded from this analysis.

Determinants: The presence/absence and titre of non-neutralizing antibodies (NNAs) will be used as the determinants.

Potential confounders: We will potentially adjust for the severity of haemophilia, FVIII genotype as well as VWF antigen levels and/or VWF activity

Endpoints: The modified bleeding severity score developed by Schulman et al [97] will be used as the endpoint (see paragraph 5.1.3).

Statistical analysis: The relationship between the presence/absence of non-neutralizing antibodies (NNAs) and bleeding severity will be assessed using linear regression.

Secondary objective 4: To evaluate potential misclassification of low-titre inhibitors as (low/high-affinity) non-neutralizing antibodies in patients with haemophilia A.

Study design and population: A cross-sectional study design will be used. The population will consist of all haemophilia A patients with NNAs in the Netherlands.

Determinant: An ELISA will be used to assess the presence of (low/high- affinity) NNAs.

Endpoint: The low-titre inhibitor assay will be used to assess low-titre inhibitor presence.

Statistical analysis: This objective will firstly be explored using descriptive statistics.

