Secondary objective 5: To evaluate the diagnostic performance of a modified FVIII ELISA for detection of FVIII-specific antibodies (inhibitors), using the Bethesda assay as the reference test.

Study design and population: A cross-sectional study design will be used. The population will consist of all haemophilia A patients in the Netherlands.

Determinant: A modified ELISA will be used to detect the presence of high-affinity IgG4 FVIII-specific antibodies.

Endpoint: The Bethesda assay will be used to assess inhibitor presence; a cut-off value of 0.6 BU will be used.

Statistical analysis: The Bethesda assay will be used as the reference test, the modified ELISA will be used as the index test. We will calculate sensitivity, specificity, (positive and negative) predictive values, (positive and negative) diagnostic odds ratios and their corresponding confidence intervals.

6.5.2 Assessing dendritic cell response and T-cell activation in the FVIII immune response:

Primary objective 1: To compare the expression of interleukin-2 and TGF-beta in monocyte-derived dendritic cells after stimulation with FVIII with and without danger signals (e.g. LPS) in patients with non-neutralizing FVIII-specific antibodies (NNAs) and patients without any current FVIII-specific non-neutralizing antibodies.

Study design and population: A case-control study design will be used. The cases will consist of 25 severe patients with NNAs that never underwent ITI. The controls will consist of 25 severe patients without any current NNAs that never underwent ITI. All haemophilia patients must have a F8 intron-22 inversion mutation. Haemophilia patients with current or previous inhibitors are excluded. **Determinant:** The expression of interleukin-2 and TGF-beta in monocyte-derived dendritic cells after stimulation with FVIII and LPS will be used as the determinant. We will isolate PBMC's from all patients, monocyte-derived dendritic cells will be cultured, we will then assess the cytokine response to FVIII/LPS using RNA sequencing.

Potential confounders: We will potentially adjust for the previous number of EDs to FVIII, FVIII genotype and family history of inhibitor formation as well as other potential genetic determinants such as HLA, IL-10, TNFα, CTLA4, HO-1 and FcgR gene polymorphisms.

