Endpoint: The presence or absence of NNAs will be used as the endpoint (coded as a dichotomous variable). Firstly, The Bethesda assay will be used to assess inhibitor presence. If negative, an ELISA will be used to detect the presence of NNAs.

Statistical analysis: We will use logistic regression to evaluate the association between interleukin-2 and the presence of NNAs and the relationship between TGF-beta and the presence of NNAs. In addition, we will examine the combined effect of increased expression of interleukin-2 and TGF-beta on the presence of NNAs using logistic regression.

Primary objective 2: To compare the regulatory T- cell count, as a proportion of all CD4+ T-cells in patients with non-neutralizing FVIII-specific antibodies (NNAs) or patients without any current FVIII-specific antibodies.

Study design and population: A case-control study design will be used. The cases will consist of 25 severe patients with NNAs that never underwent ITI. The controls will consist of 25 severe patients without any current NNAs that never underwent ITI. All haemophilia patients must have a F8 intron-22 inversion mutation. Haemophilia patients with current or previous inhibitors are excluded. **Determinant:** T-regulatory cell count, as a proportion of all CD4+ T-cells will be used as the determinant. T-regulatory cell count will be assessed using both flow cytometry and a quantitative real-time PCR assay developed by Epiontis (Epiontis Treg assay).

Potential confounders: We will potentially adjust for the previous number of EDs to FVIII, FVIII genotype and family history of inhibitor formation as well as other potential genetic determinants such as HLA, IL-10, TNF α , CTLA4, HO-1 and FcgR gene polymorphisms.

Endpoint: The presence or absence of NNAs will be used as the endpoint. Firstly, The Bethesda assay will be used to assess inhibitor presence. If negative, an ELISA will be used to detect the presence of NNAs.

Statistical analysis: We will use logistic regression to evaluate the association between the dendritic cell cytokine response and the presence/absence of NNAs

Chapter 7 - Ethical considerations

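### NNA status rests on Bethesda (cut-off 0.6 BU) and ELISA alone, so patients with an inhibitor below 0.6 BU can be classed as NNA, including among the 25 cases, although a planned low-titre assay could identify them

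*Protocol*

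**What the plan says.** - **Case definition, 6.5.2, primary objectives 1 and 2.** NNA status is set in sequence: "Firstly, The Bethesda assay will be used to assess inhibitor presence. If negative, an ELISA will be used to detect the presence of NNAs". Each objective compares 25 severe cases with NNAs and 25 severe controls without.
- **Exclusion, same objectives.** "Haemophilia patients with current or previous inhibitors are excluded". No separate assay is named for this exclusion.
- **6.5.1, primary objective 1 (prevalence).** The same order applies after the Bethesda assay: "If negative, the presence and characteristics of NNAs will be assessed using an ELISA platform". The population is haemophilia A patients without current inhibitors.
- **6.5.1, primary objective 2 (Ig class, IgG subclass, affinity).** The inhibitor and NNA groups are again formed from Bethesda and ELISA.
- **Cut-offs, 5.1.2.** "A titre of at least 0.6 Bethesda Units is required to be positive for this assay". In addition: "The cut-off point for low-titre vs high-titre inhibitors is 5.0 Bethesda Units".
- **Low-titre assay, 5.1.2.** It is listed among the tests on first-visit blood: "To assess the presence of low-titre inhibitors, we will use a lowtitre inhibitor assay".
- **Stated reason, 1.5.1.** "The HiN-6 will also assess possible misclassification of low-titre inhibitors as non-neutralizing antibodies using a low-titre inhibitor assay". Sections 2.5.1 and 6.5.1 repeat this as secondary objective 4, in all haemophilia A patients with NNAs: "The low-titre inhibitor assay will be used to assess low-titre inhibitor presence". The only analysis named there is descriptive.

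**The concern.** The protocol recognises that some patients labelled NNA may really carry a low-titre inhibitor, and it plans the assay that would show this. Yet the NNA group is formed before that result is considered, and nothing feeds the result back into a case definition, an exclusion or a primary analysis.

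Three results are exposed:

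- **6.5.2.** The cases are meant to have NNAs and no inhibitor. If some carry an inhibitor below 0.6 BU, a cytokine or regulatory T-cell difference is harder to read as specific to NNAs.
- **6.5.1, primary objective 2.** Section 1.5.1 describes IgG4 and high affinity as features associated with neutralizing antibodies. If undetected inhibitors share those features, having them in the NNA group blurs the very contrast under study.
- **6.5.1, primary objective 1.** NNA prevalence among non-inhibitor patients would be overstated.

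**Working it through.** **1. The plan's own figure.** 25 cases + 25 controls = 50, which matches the 50 second-visit participants in 5.1.2. The protocol gives no alpha, power or effect size for 6.5.2, so there is no power figure to reproduce.

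**2. The rules side by side.** Take an ELISA-positive patient and vary the inhibitor level.

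| Inhibitor level | Bethesda | Status under the written rule | Status under secondary objective 4 |
|---|---|---|---|
| 0.6 BU or more, including the low-titre range up to 5.0 BU | positive | inhibitor; excluded from 6.5.2 | not at issue |
| below 0.6 BU, low-titre assay positive | negative | NNA; can be a case | low-titre inhibitor misclassified as NNA |
| none detected by either assay | negative | NNA; can be a case | NNA |

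Only the middle row is affected.

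**3. Timing.** The low-titre assay uses first-visit blood. Section 5.1.2 says the 50 second-visit participants are chosen from the results of the first analyses. The low-titre result could therefore be on hand at selection, but no rule says that it is used.

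**4. Illustrative size.** Let m be the share of Bethesda-negative, ELISA-positive patients who are positive on the low-titre assay. The protocol does not give m, so 2% to 30% is assumed. Let p be the Bethesda-only NNA prevalence, also not given; 0.2 is assumed.

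- Expected affected cases = 25m.
- Chance of at least one = 1 − (1 − m)^25, treating cases as independent.
- Prevalence ratio: among N Bethesda-negative patients, pN are called NNA, and pmN of these are low-titre positive. Removing them as inhibitor patients takes them out of the numerator and the non-inhibitor denominator, which gives p(1 − m)/(1 − pm). The ratio of stated to corrected prevalence is (1 − pm)/(1 − m). This counts only low-titre positives who are also ELISA positive.

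| m | 25m | P(at least one) | (1 − pm)/(1 − m) at p = 0.2 |
|---|---|---|---|
| 0.02 | 0.5 | 0.40 | 0.996/0.98 = 1.02 |
| 0.05 | 1.25 | 0.72 | 0.99/0.95 = 1.04 |
| 0.10 | 2.5 | 0.93 | 0.98/0.90 = 1.09 |
| 0.20 | 5 | 0.996 | 0.96/0.80 = 1.20 |
| 0.30 | 7.5 | >0.999 | 0.94/0.70 = 1.34 |

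**The case against.** **Inhibitor is an operational term here.** Section 5.1.2 and the Chapter 6 endpoints tie inhibitor presence to the Bethesda assay. The instruction sheet in Appendix 1 also defines inhibitor development by that assay and treats only titres of at least 0.6 BU, documented twice, as relevant. On that reading the exclusion and the case definition in 6.5.2 agree. This stands to the extent that a reader might infer a plain breach of the exclusion, and the text does not support that. It does not remove the point: if nothing below 0.6 BU counted as an inhibitor, secondary objective 4 would have nothing to call misclassified.

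**The issue is already being studied, with a little-documented assay.** The low-titre assay is sourced to a personal communication, with no cut-off or performance given. Keeping Bethesda as the reference is defensible, and this is a good reason to report both definitions. It is not a reason to leave the result unused when cases are picked.

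**A sensitivity analysis could sit in a statistical analysis plan that is not shown.** That is true for 6.5.1. In 6.5.2 the rule decides who is invited to give more blood, and the protocol fixes it. After the second visits, an analysis plan can drop cases from the 25 but cannot replace them.

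**The aim in 1.5.2 is broader.** It concerns FVIII-specific antibody formation in general, and a patient with an inhibitor below 0.6 BU is still an antibody-former. This stands: the broad aim survives, and what weakens is the reading specific to NNAs. To say that a difference could not be attributed at all would go too far.

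**The share m has no source.** This also stands. It may differ between settings, since 6.5.2 removes previous inhibitors as well as current ones, while 6.5.1 primary objective 1 removes only current ones.

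**Conclusion.** The point holds as a gap between the NNA definition and the protocol's own account of misclassification. Under the plan as written, patients with an inhibitor below 0.6 BU can be classed as NNA in both 6.5.2 objectives and in 6.5.1 primary objectives 1 and 2. This conclusion rests on the text and does not depend on m.

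The size is unknown. At an assumed m of 2% to 30%, 0.5 to 7.5 of 25 cases would be affected. With an assumed p of 0.2, prevalence would be overstated 1.02 to 1.34 times.

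Three stronger readings are not supported:

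- That such patients will enter the case group. The protocol calls the misclassification only possible or potential.
- That all low-titre inhibitors are affected. Those from 0.6 to 5.0 BU are Bethesda positive and already excluded.
- That prevalence is inflated by 1/(1 − m), which would be 1.43 at m = 0.3. That formula leaves low-titre positives in the non-inhibitor denominator.

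This is a change worth making before second-visit sampling, because it is cheap then and hard to repair afterwards.

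**What to change.** - **6.5.2 and the second-visit selection in 5.1.2.** Require the low-titre result before participants are chosen. Define an NNA case as ELISA positive, Bethesda below 0.6 BU and negative on the low-titre inhibitor assay.
- **6.5.1, primary objectives 1 and 2.** Report low-titre-positive patients as a separate category. Give results under the Bethesda-only definition and under the definition that also needs a negative low-titre assay.

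Cost: protocol wording and the order of laboratory work. No new assay or blood draw is needed, and the planned 25 + 25 is unchanged. There are two downsides: the pool of eligible cases becomes slightly smaller, and case selection comes to depend on an assay whose performance the protocol does not document. In 6.5.1, reporting both definitions lets readers see how far the results rest on that assay.

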7.1 Regulation statement

The study will be conducted according to the principles of the Declaration of Helsinki (seventh revision, 2013) and in accordance with the Medical Research Involving Human Subjects Act (WMO). In addition, this study will also be conducted according to Good Research Practice (GRP) in accordance with the Law for the Protection of Personal Data (WBP) and the Law for Agreement on Medical Treatment (WGBO).

7.2 Recruitment and consent

All patients will be recruited through their own physician. Via the physician, all patients will be sent

HiN-6 study

an invitation letter, including a patient information letter and an informed consent form. Patients will be asked to provide consent for the questionnaire first. At the clinic the informed consent form will be signed by both the participant and the physician, before data collection and sampling of blood/urine takes place. Patients will be given 1 month to reply for participation in the questionnaire. If no response is received after 1 month (either refusal or consent), a second letter will be sent. Persistent non-responders will be asked to participate at the next appointment with their treating physician. If the next appointment is more than 3 months away, patients will be contacted by phone. Patients with questions regarding the study will be given the option to contact their treatment centre or the research team for further information. If a participant is a minor between 12-17 years old, the parents/legal guardian(s) will also need to consent. If a participant is a minor under 12 years, only the parents/legal guardian(s) will be asked to formally consent.

